### 3. SUMMARY OF STUDY PLAN

**3.1 Study design:** We propose a randomized, double-blind, placebo-controlled pre-surgical trial of 0.228% 4-hydroxy-tamoxifen (4-OHT) gel vs. oral tamoxifen (TAM) 20 mg daily in up to 108 women with a core needle biopsy diagnosis of ER positive DCIS, regardless of grade, with 1:1 randomization to oral TAM and 4-OHT gel. We will consider the following strata: 1) Recruitment site, of which there will be seven, and 2) Pre- or post-menopausal status, within each site. The 4-OHT group will apply active gel 2 mg daily to each breast and take oral placebo for a minimum of 4 and a maximum of 10 weeks. The TAM group will take 20 mg TAM orally daily and apply gel placebo daily to each breast for 4 to 10 weeks. The primary endpoint is Ki67 labeling index in the DCIS core (pre-therapy sample) compared to the surgical sample (post-therapy sample), with the expectation that the reduction in this parameter will be equivalent in the two arms.

**3.2 Number of participants to be enrolled:** A maximum of 108 participants with estrogen receptor (ER) positive DCIS of the breast, newly diagnosed on core needle biopsy, will be accrued into two intervention arms: oral tamoxifen 20 mg daily, and 4-hydroxytamoxifen gel, 4 mg daily (2 mg to each breast). Due to early drop-out after randomization, we expect no more than 100 women to start intervention. In addition, we assume that there will be an attrition of 10 women (10%) related to lack of compliance to medication or other logistical reasons, and an attrition of another 10 women (10%) related to lack of sufficient DCIS tissue for analysis of the primary endpoints. Therefore a total of 90 women (45 in gel arm and 45 in oral arm) will be evaluated for study endpoints, and 80 women (40 per arm) will provide data for the primary endpoint. Assuming a screening rate of approximately 60 participants per month and an average accrual rate of 4.5 participants per month, we expect the study to be complete within 24 months. Accrual is competitive and sites should accrue as many participants as possible until total accrual is met.

**3.3 The study population:** newly diagnosed adult DCIS patients will be enrolled at 7 centers. Eligible participants will be approached following diagnostic core needle biopsy at the time of initial surgical consultation. The centers are:

- Northwestern University/Northwestern Medicine (NU)

- Duke University Medical Center (DUMC)

### *3.4 Intervention plan*

The intervention phase for consenting participants will begin within 5 business days following randomization and end on the day prior to surgery. At baseline (Screen 1) visit, participants will be given 120 placebo or active capsules (20 mg tamoxifen) and two canisters of placebo or active 4-OHT gel, each containing 80 reliable doses. Participants will take study agent for a minimum of 4 and a maximum of 10 weeks. The intervention phase for consenting participants will begin within 5 business days following randomization and end on the day prior to surgery. The 4-OHT group will apply active gel 2 mg daily to each breast and take oral placebo daily for 4 to 10 weeks. The TAM group will take 20 mg TAM orally daily and apply gel placebo daily to each breast for 4 to 10 weeks. There will be two study visits, the day of surgery and the post-op visit.

If a participant opts to proceed to surgery prior to the planned end of intervention, but has completed 4 weeks of intervention she will be asked to complete all study visits/procedures as specified in section 3.8, and she will be included in the final statistical evaluation.

### *3.5 Run-in procedures*

No run-in period is planned

### *3.6 Assessment time points are:*

- 3.6.1 Baseline ..... (Screen 1 visit)
- 3.6.2 Day of surgery ..... (Study Visit 1, post-intervention sample collection)
- 3.6.3 Post-operative visit ..... (Study Visit 2, symptom assessment)

### *3.7 Description of measurements taken to meet study objectives*

*Screen 1:* at entry, for consent, medical history including date of last period and menopause determination, pregnancy test (if needed), breast cup size, body mass index, explanation of gel application, baseline symptom assessment (BESS questionnaire), and blood draw. After randomization, the study coordinator will request the paraffin blocks of the diagnostic core needle biopsy (DCNB). The study consent will include specific permission from the subject, to allow the DCNB block, and a selected surgical block to be released to Northwestern University (NU). These will be mailed to NU per instructions in the lab manual. Institutions that do not allow release of DCNB blocks, will provide multiple unstained sections of the DCNB block as detailed in Section 10.2.3.

*Study Visit 1:* on the day of surgery for blood draw, BESS questionnaire, medical history, symptoms assessment, and collection of surgical tissue sample (since the blood and surgical samples must be collected on the same day). Breast adipose and parenchymal tissue excised from multiple locations will be snap frozen with liquid nitrogen and stored at -80°C for measurement of TAM metabolites. A portion of each sample will be formalin-fixed for assessment of tissue composition (see Section 10 and Figure 2A).

*Study Visit 2:* the post-operative visit, up to 21 days post-surgery, to document resolution of study related

symptoms. Visit 2 will also serve as the trigger for the study coordinator to request the paraffin blocks of the surgical sample, since the final pathology report will have been issued at this point. These will be mailed, along with other study samples, in a single shipment as each participant completes the study, per instructions in the lab manual. Institutions that do not allow release of paraffin blocks, will provide multiple unstained sections of the paraffin block as detailed in Section 10.2.3. A final phone call will be made up to 35 days following Study Visit 2 to premenopausal women whose last menstrual period did not occur between surgery and Study Visit 2.

### 3.8 *Handling of subjects who elect not to complete protocol-specified therapy.*

Every attempt will be made to retain all subjects for the entire duration of protocol-specified therapy. However, some participants may opt for early surgery. In this case, endpoints will be measured if more than 4 weeks of therapy have been completed (blood, tissue biomarkers and drug concentrations).

3.9 *Safety monitoring:* since oral tamoxifen is a widely used agent with a well-known safety/toxicity profile, we have been able to define exclusion criteria to avoid women for whom there will be safety concerns (e.g. those with a history of thromboembolism, and current smokers). Given the duration of intervention (maximum 10 weeks) it will not be necessary to use laboratory tests to monitor toxicity of oral tamoxifen other than the comprehensive chemistry panel at the pre- and post-treatment visits. The safety of the 4-OHT gel is also well established, since it is a metabolite of tamoxifen; the only unique toxicity to be expected would be skin irritation, which was observed for one participant in our previous trial, and has been reported to be infrequent in other, larger studies [39].

3.10 *Duration of study:* we anticipate that overall recruitment will cover months 1-24. The last subject should complete participation by month 27. Data assembly, cleaning, and biomarker evaluation will occur in months 24-36.

## 4. PARTICIPANT SELECTION

### 4.1 Inclusion Criteria

4.1.1 Screen-detected, ER positive DCIS of the breast proven on core needle biopsy, defined as 10% ER positive cells. Microinvasion will be allowed. The size of the DCIS in the core biopsy sample must be at least 4mm for a single core or total at least 5 mm if multiple cores are summed and must be estimated on the deepest step section (if step sections are taken).

4.1.2 Age  $\geq 18$  years. DCIS of the breast is almost exclusively an adult condition. Because no dosing or adverse event (AE) data are currently available on the use of tamoxifen in participants  $<18$  years of age, children are excluded from this study.

4.1.3 ECOG performance status  $\leq 1$  (Karnofsky  $\geq 70\%$ ; see Appendix A)

4.1.4 Participants must have acceptable organ and marrow function as defined below: Baseline lab parameters are not standard of care for initiation of tamoxifen therapy; a minimal panel will therefore be appropriate.

Leukocytes	$\geq 3,000/\text{microliter}$
Platelets	$\geq 100,000/\text{microliter}$
Total bilirubin	$\leq 1.5 \times$ institutional upper limit of normal (ULN)
AST (SGOT)/ALT (SGPT)	$\leq 1.5 \times$ ULN
Creatinine	$\leq 1.5 \times$ ULN

4.1.5 The effects of topical 4-OHT gel on the developing human fetus at the recommended therapeutic dose are unknown. For this reason and because tamoxifen is known to be teratogenic, all heterosexually active women who may become pregnant must agree to use a reliable non-hormonal contraceptive method or a hormonal IUD during the study and for 2 months after completing study medications. Reliable nonhormonal methods of contraception include barrier contraception and an Intra-Uterine Device (IUD). Hormonal IUDs are also allowable methods of birth control. [Note: Women who had tubal ligation or had a partner who had undergone a vasectomy (and are monogamous) are eligible for the study and are not required to use barrier contraception.]

4.1.6 Willingness to avoid exposing breast skin to natural or artificial sunlight (i.e. tanning beds) for the duration of the study.

4.1.7 Ability to understand and the willingness to sign a written informed consent document.

## **4.2 Exclusion Criteria**

4.2.1 Exogenous sex steroid use within 4 weeks prior to diagnostic core needle biopsy (DCNB). Use of vaginally administered estrogens and hormone coated IUD such as Mirena is permitted and use should continue until surgery.

4.2.2 History of any prior ipsilateral breast radiotherapy. Previous unilateral radiation of the contralateral side is allowed.

4.2.3 History of other prior breast cancer-specific therapy within the previous 2 years (chemotherapy, anti-HER2 agents, endocrine agents, everolimus, CDK4-6 inhibitors).

4.2.4 Skin lesions on the breast that disrupt the stratum corneum (eg eczema, ulceration).

4.2.5 History of endometrial neoplasia

4.2.6 History of thromboembolic disease (history of varicose veins and superficial phlebitis is allowed)

4.2.7 Current smokers.

4.2.8 Current users of potent inhibitors of tamoxifen metabolism must be willing and able to discontinue use and switch to an alternative medication for the duration of participation, under the advice of their physician. If the physician believes the current medication is medically necessary, the participant will not be eligible. The potent inhibitors of tamoxifen metabolism are: bupropion, cinacalcet, fluoxetine, paroxetine, quinidine.

4.2.9 Prior use of SERMS or AIs including tamoxifen, raloxifene, anastrozole, letrozole, or exemestane for prevention or therapy within 5 years.

4.2.10 Participants may not be receiving any other investigational agents within 30 days of enrollment or during this study.

4.2.11 History of allergic reactions attributed to tamoxifen or compounds of similar chemical or biologic composition.

4.2.12 Uncontrolled intercurrent illness including, but not limited to, ongoing or active infection, symptomatic congestive heart failure, unstable angina pectoris, cardiac arrhythmia, or psychiatric illness/social situations that would limit compliance with study requirements.

4.2.13 Pregnant women are excluded from this study. Because there is an unknown but potential risk for AEs in nursing infants secondary to treatment of the mother with tamoxifen, breastfeeding should be discontinued by nursing mothers who agree to participate in the study.

4.2.14 Men are excluded from this study since DCIS of the breast is exceedingly rare in men, and there are no data regarding skin penetration of 4-OHT though male chest wall skin (which is thicker and hairier than female chest wall skin).

### **4.3 Inclusion of Women and Minorities**

Women of all races and ethnic groups are eligible for this trial. Men are not included since DCIS of the breast is exceedingly rare in men, and there are no data regarding skin penetration of 4-OHT though male chest wall skin (which is thicker and hairier than female chest wall skin).

### **4.4 Recruitment and Retention Plan**

4.4.1 Recruitment brochures and a DCIS Fact Sheet will be developed and approved by the Central Institutional Review Board (CIRB); these materials will be posted in the breast center waiting rooms at each institution, the mammography waiting rooms, the cancer center and institutional websites, and advertised through Google ads. Physician letters will be sent to the referral base at each institution.

4.4.2 Recruitment to similar studies is well established at the seven participating institutions, and will be standardized as far as possible. In brief, the breast surgery clinic schedule will be screened by the study coordinator 2-3 days ahead of the scheduled consultation visit. The medical records of newly diagnosed DCIS patients will be reviewed, if preliminary eligibility criteria are met, pre-screening will be initiated. The coordinator will contact the radiologist and pathologist reviewing the case to assess quality of diagnostic films, and the treating physician regarding suitability of the patient as a potential participant. The coordinator will then be present at the visit of the patient who appears eligible on pre-screen, and once the surgeon has broached the study to the patient, the coordinator will approach the potential participant to provide more information, including the informed consent document. The treating physician will have to remain involved in this process, advising and encouraging the patient as needed. All efforts will be made to align the study visits with usual care visits so as to reduce the burden of the study on the patient.

4.4.3 The proposed study intervention is 4 to 10 weeks prior to surgery, which is a reasonable time frame for newly diagnosed DCIS patients. All of the study materials will explain to subjects why a little delay is not felt to be a safety concern.

4.4.4 Retention is not expected to be a challenge as coordinators will make periodical phone calls to monitor compliance and address subjects' concerns. The phone app used in a previous topical gel study will be modified for this study, and will aid in retention.

4.4.5 Recruitment and retention experience at each institution will be reviewed at monthly conference calls of the site PIs and coordinators, and through AQUIP reports, to identify problems and successful strategies. If protocol-related barriers are identified, strong consideration will be given to protocol revision to address these (unless this would compromise the scientific integrity of the study).

## **5. AGENT ADMINISTRATION**

Intervention will be administered on an outpatient basis. Reported AEs and potential risks are described in Section 6.2.

### **5.1 Dose Regimen and Dose Groups**

Experimental Arm: (Group 1)

4-hydroxytamoxifen gel applied to both breasts (2mg/breast) daily

Oral placebo taken daily

4 to 10 weeks of treatment between randomization and surgical resection

Control Arm: (Group 2)

Placebo gel applied to both breasts daily

20mg oral tamoxifen taken daily (taken as one 20mg capsule)

4 to 10 weeks of treatment between randomization and surgical resection

### **5.2 Tamoxifen and 4-OHT gel Administration**

Participants will self-administer the oral tamoxifen/placebo capsules and 4-hydroxytamoxifen/placebo gel. Participants will be asked to take oral and topical dosing at the same time, preferably in the morning, for consistency and comparable pharmacokinetics. The subjects will be instructed to take the study capsule with some water around the same time every day. The gel will be applied daily to both breasts, freshly washed, either by hand washcloth, shower, or bath, preferably in the morning (in order to minimize potential transfer to the partner at night). If morning shower is not possible, the subject will wash the breasts with a washcloth before gel application, to remove the prior day's dose. If a morning swim is planned, application should be after swim. No washing or immersion in water should occur for at least 4 hours following gel application. The timing of administration of capsule and gel should be as close to each other as possible (to aid memory). The gel should not be used near fire, flame or while smoking since it is flammable due to alcohol. Once dry, the gel is no longer flammable. Detailed instructions regarding application are in Appendix B and a demonstration of gel application will occur during the Screen 1 visit. The treated breasts should be covered at all times to avoid transfer to other people and protect from natural or artificial sunlight; contact is permitted after the treated area has been washed with soap and water and washing is allowable after a minimum of 4 hours post-application.

Each 4-OHT gel canister will contain 80 reliable doses of product metered to dispense 1mL per actuation, 2mg of 4-OHT gel per actuation (~40 days of therapy). The dose is 2mg (1mL) per breast, 4mg (2mL) total per day. A kit containing two canisters of 4-OHT/placebo gel and one bottle of 120 tamoxifen/placebo capsules will be given/shipped to the patient at the time of randomization.

### **5.3 Run-in Procedures**

No run-in phase is planned.

### **5.4 Contraindications**

Participants are to avoid exposure of the treated breast skin to natural or artificial sunlight. This includes sunbathing or the use of tanning beds with the breasts exposed. Also, women who have dermatologic conditions causing the breakdown of skin in the area of gel application should not use 4-OHT gel.

## **5.5 Concomitant Medications**

All medications (prescription and over-the-counter), vitamin and mineral supplements, and/or herbs taken by the participant will be documented on the concomitant medication CRF and will include: 1) start and stop date, dose and route of administration, and indication. Medications taken for surgery should not be included.

## **5.6 Dose Modification**

None planned

## **5.7 Adherence/Compliance**

5.7.1 Participants will be considered compliant if they have taken 80% of the prescribed doses and have missed no more than 3 doses in the final 14 days prior to surgery.

5.7.2 The participants will be asked at registration if they would like to utilize a phone application in place of paper forms. According to subject preference, participants will either utilize phone application or fill out paper forms daily to monitor compliance. For participants utilizing the phone application, the study coordinator will be notified after 2 days of missed entries. For individuals using paper forms, email messages will be sent daily for the first week; in following weeks, messaging will be targeted to women having difficulty remembering their dose.

5.7.3 Capsule counts and weighing of gel dispensers will be performed at the conclusion of therapy. Drug and metabolite levels will be measured in blood and tissue on the last day of administration. Prescribed doses include one capsule per day, or one pump of the gel on each breast per day. If the capsule count consumed by the subject is lower than  $D*80\%$ , or the amount of gel consumed is less than  $2D*80\%*[m - sd(m)]$ , where D is the number of days between visits, m and  $sd(m)$  are the mean and standard deviation of the weight of one pump of the gel provided by the manufacturer, or if more than three doses of therapy are missed during the final 14 days, the subject will be considered non-compliant. For subjects with only one breast, the lower limit of the amount of gel consumed for compliance is  $D*80\%*[m - sd(m)]$ . All participants who receive a study agent for any period of time will be evaluable for toxicity. Treatment compliance assessment will be based on the active ingredient component of the treatment regimen, i.e. the pill count for the Oral Tamoxifen group and gel dispenser weight for the 4-OHT gel group.

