#### Role of tamoxifen therapy for women with DCIS

Tamoxifen (TAM) has been proven to reduce risk of both local recurrence and new primary breast cancer in women with DCIS, providing both preventive and therapeutic benefit [9, 10]. Oral TAM also has proven risk reduction value for women at increased risk for breast cancer, numbering over a million women in the United States alone [11, 12]. However, tamoxifen acceptance by DCIS and high-risk patients has been lower than expected, mainly because of toxicity concerns [13-16]. Serious adverse effects of TAM are related to its estrogen agonist activity on the endometrium, leading to an increased risk of endometrial cancer in postmenopausal women; and the activation of coagulation pathways leading to an increased risk of thromboembolism [11]. Hot flashes and vaginal symptoms were 20-30% more common in women aged 35-49 on tamoxifen than in the placebo group of the BCPT [17]. Together, these side effects are significant barriers to wide acceptance of TAM by DCIS patients [13] and high-risk women [18]. Although aromatase inhibitors are now proven to be efficacious for post-menopausal women [19, 20], these too have a burden of skeletal and possibly cardiovascular toxicity. There are no endocrine agents close to Phase 3 testing for pre-menopausal women. A particular challenge for primary and secondary breast cancer prevention efforts, therefore, is to devise an efficacious and non-toxic intervention which is likely to be widely accepted by women with DCIS and those at high risk for developing breast cancer. A potential solution is the development of delivery methods that preserve efficacy through targeted local delivery to the breast, but minimize toxicity because of low systemic exposure, as discussed in Sections 2.2 and 2.3.

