
**Adverse Events.** AEs will be assessed using CTCAE. Worst grade toxicity for each AE type will be summarized by arm using descriptive statistics. For each AE type, proportions of patients experiencing toxicity of any grade will be compared between arms using Fisher's exact test.

**Treatment Compliance.** Compliance will be defined as described in Section 5.7. Each patient will be determined as compliant or non-compliant for each treatment component (capsules compliance and gel compliance). Treatment compliance rates based on active ingredient component will be summarized using proportions, and compliance rates will be compared between arms using Fisher's exact test. In addition, in order to determine whether compliance is different for capsule vs. gel administration, within-subject differences in treatment component compliance will be analyzed using the McNemar test among all patients, regardless of treatment arm.

**Subgroup analysis.** Exploratory analyses will be conducted by menopausal status (pre or peri-menopausal vs. post-menopausal). Descriptive statistics will be used to summarize study endpoints by group. In addition, linear regression models as described above will be used with the addition of menopausal status and possibly its interaction with treatment as predictors. Model-based linear contrasts will be constructed to test relevant treatment noninferiority or superiority hypotheses within subgroups. Similar analyses will be conducted in the subgroup of women with invasion in the post-treatment surgical sample.

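### The only between-arm compliance test sets tamoxifen capsule counts against 4-OHT gel weights; it describes active-drug exposure but cannot be read as adherence or tolerability, and like-with-like comparisons should be added

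*Combined protocol and SAP*

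**What the plan says.** The trial is double-dummy. Section 3.1 states for one arm "The 4-OHT group will apply active gel 2 mg daily to each breast and take oral placebo", and for the other "The TAM group will take 20 mg TAM orally daily and apply gel placebo daily to each breast".

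Section 5.7.3 gives a cut-off for each product. Capsules fail below 80% of D, the number of days between visits. Gel fails below 2D × 80% × [m − sd(m)], where m and sd(m) are the manufacturer's mean and standard deviation for the weight of one pump. Missing more than three doses in the last 14 days also fails. The section then bases the assessment on the active product: "the pill count for the Oral Tamoxifen group and gel dispenser weight for the 4-OHT gel group".

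Under Treatment Compliance, section 13.5.4 says: "Each patient will be determined as compliant or non-compliant for each treatment component (capsules compliance and gel compliance"). It plans two tests:

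- Between arms: "Treatment compliance rates based on active ingredient component will be summarized using proportions, and compliance rates will be compared between arms using Fisher's exact test".
- Capsule against gel: "within-subject differences in treatment component compliance will be analyzed using the McNemar test among all patients, regardless of treatment arm".

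No between-arm test of the same product is planned, neither tamoxifen against placebo capsule nor 4-OHT against placebo gel. Section 13.4.2 also uses the section 5.7 definition for the per-protocol population.

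**The concern.** The trial's rationale is partly about acceptability. Section 2.1 says that "tamoxifen acceptance by DCIS and high-risk patients has been lower than expected, mainly because of toxicity concerns", and section 2.3.3 expects less severe symptoms on the gel. A between-arm compliance result will naturally be read in that light.

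The planned contrast does not support that reading. One side is an active capsule that is counted; the other is an active gel that is weighed. A null result could hide two real effects of similar size. A significant result could come from the product or the measuring rule alone. Randomisation makes the arms comparable on each product, but the planned test compares different products and so does not use that.

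**Working it through.** **Inputs from the documents.** 1:1 allocation (13.1). No more than 100 women are expected to start (13.2), so about 50 per arm. Cut-offs are from 5.7.3. Section 6.6 has dispensers weighed by the pharmacy at dispensing. Appendix B has the participant prime each canister by pressing the pump several times and not use the first dose.

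**Assumed, because the documents give none.** Compliance rates; two-sided 0.05 for the compliance test; the coefficient of variation (CV) of pump weight; the number of pumps' worth of gel lost in priming. There is no stated figure on this point to reproduce.

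**1. What the Fisher test estimates.** Let p be compliance with placebo capsules, t the loss in capsule-taking due to tamoxifen, and b the loss due to gel burden, any 4-OHT effect and the weighing rule, taken as additive. Then

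- tamoxifen arm, capsule: p − t
- 4-OHT arm, gel: p − b
- planned difference: (p − t) − (p − b) = b − t

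Only b − t can be estimated, and it is zero whenever b = t.

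**2. The measuring rules differ.** As a share of nominal consumption, the capsule cut-off is 80% and the gel cut-off is 80% × (1 − CV):

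| Assumed CV | Gel cut-off |
|---|---|
| 0% | 80% |
| 2% | 78.4% |
| 5% | 76% |
| 10% | 72% |

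Gel lost in priming leaves the dispenser after the starting weight is taken, so it counts as used. The diary asks about discarded pumps, but the 5.7.3 formula does not subtract them. Applied pumps needed to pass = 2D × 0.8 × (1 − CV) − (canisters × priming pumps). With CV 5%:

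| Days, canisters | Priming pumps lost per canister | Applied pumps needed | Share of prescribed |
|---|---|---|---|
| 28, one | 1 | 42.56 − 1 = 41.6 of 56 | 74% |
| 28, one | 3 | 42.56 − 3 = 39.6 of 56 | 71% |
| 70, two | 1 | 106.4 − 2 = 104.4 of 140 | 75% |
| 70, two | 3 | 106.4 − 6 = 100.4 of 140 | 72% |

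On the weight rule, a woman can therefore pass on gel with fewer doses than she would need on capsules.

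**3. Size of the effect on the test.** Exact Fisher power, summing over all binomial outcomes, 50 per arm, p = 95%:

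| Assumed losses | Planned test | Chance of p ≤ 0.05 | Capsule v capsule | Power |
|---|---|---|---|---|
| t = 10, b = 10 points | 85% v 85% | 2.4% | 85% v 95% | 24.4% |
| t = 20, b = 20 | 75% v 75% | 3.0% | 75% v 95% | 74.8% |
| t = 0, b = 20 | 95% v 75% | 74.8% | 95% v 95% | 0.7% |

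The first two rows show cancellation. The third shows a significant arm difference with no drug effect.

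**4. The pooled McNemar test.** Its behaviour depends on which product side effects reduce. With t = b = 10:

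- Tamoxifen lowers capsule-taking only. Tamoxifen arm: capsule 85%, gel 85%, difference 0. 4-OHT arm: 95%, 85%, difference 10. Pooled: (0 + 10)/2 = 5 points, against a true product effect of 10.
- Tamoxifen lowers both products equally. Tamoxifen arm: 85%, 75%, difference 10. 4-OHT arm: 95%, 85%, difference 10. Pooled: 10 points, with no drug effect mixed in.

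Under either pattern, the test gives no between-arm comparison of one product, and the capsule-v-gel difference still includes the difference in measuring rule.

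**The case against.** **The test answers a different question.** Section 13.5.4 labels the comparison as based on the active ingredient, and asks whether each arm took its assigned active drug. That is useful for exposure and for the per-protocol set, and neither 5.7 nor 13.5.4 calls it a test of tolerability. This stands: the definition is not at fault. What is missing is the comparison that would answer the adherence question.

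**Tolerability is compared elsewhere.** The BESS questionnaire, Fisher tests on each adverse event type, and the coagulation and estrogenic markers all compare the arms, and compliance is not a listed objective or endpoint. This stands too and limits the weight of the point. None of those measures shows whether women took the products.

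**The McNemar test covers product burden.** In part it does. A reader might infer that about half of any tamoxifen-driven non-adherence must appear there as a product effect. The documents do not support that: it holds only if tamoxifen reduces capsule-taking and leaves gel-taking untouched. Women are blinded, products match, and section 5.2 asks for both at the same time, so side effects might reduce both equally.

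**The rates are constructed.** They are. A reader might infer from section 2.1 that cancellation is to be expected here. That passage concerns acceptance of tamoxifen generally and gives no adherence figure for 4 to 10 weeks of blinded treatment. Section 2.3.2 reports good compliance in the earlier DCIS trial. The figures show what the test can do, not what it will do.

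**The added tests have little power for small effects.** True: 24.4% for 95% v 85%. The main gain is an interpretable estimate with its interval.

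**Conclusion.** The point holds for the between-arm Fisher test. It estimates b − t, a mixture of drug, product and measuring rule, and should be read only as a description of active-drug exposure. The lower gel cut-off follows from the protocol's own formula whenever sd(m) is above zero; its size depends on an sd(m) and a priming loss that the documents do not give. The rejection rates of 2.4% (10-point losses that cancel) and 74.8% (20-point gel loss, no drug effect) rest on the assumed rates, additivity, 50 per arm and two-sided 0.05.

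For the pooled McNemar test the claim is conditional: a drug effect enters only if tamoxifen side effects reduce capsule-taking more than gel-taking.

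This is a secondary matter. It does not affect the primary endpoint or its stated 80.5% power, and active-component scoring remains reasonable for exposure and for the per-protocol set.

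**What to change.** In section 13.5.4, under Treatment Compliance:

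1. Add capsule compliance between arms (tamoxifen v placebo capsule) and gel compliance between arms (4-OHT v placebo gel), each as a difference in proportions with a confidence interval and Fisher's exact test.
2. Report the within-woman capsule-v-gel comparison by arm as well as pooled.
3. Keep the active-component rates, and state that they describe exposure to active drug and define the per-protocol set, and are not a comparison of adherence or tolerability.

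The cost is a few sentences of analysis-plan wording and a small table. Every woman is already to be classified on both products, so no new data are needed and the sample size does not change.
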